- A. Obtain information by intervening or interacting with living individuals for research purposes*
- B. Obtaining identifiable private information about living individuals*
- C. Obtaining the voluntary informed consent of individuals to be subjects*
- D. Makes decisions about subject eligibility*
- E. Studying, interpreting, or analyzing identifiable private information or data/specimens for research purposes*
- F. Studying, interpreting, or analyzing de-identified data or specimens for research purposes*
- G. Some/all research activities performed outside NIH*

Investigational Agents:

Drug Name:	[¹⁸ F] Fluoromisonidazole, 1 H-(3-[¹⁸ F]-fluro-2-hydroxyl-propyl)-2-nitro-imidazole, [¹⁸ F] FMISO
IND Number:	124706
Sponsor:	[name]
Manufacturer:	Cardinal Health

Abbreviated Title: [¹⁸F]-FMISO Imaging Post TACE

Version Date: 08/31/2016

PRÉCIS

Background

- TACE is the standard therapy for inoperable primary liver cancers or tumor control prior to transplantation. The mechanisms for TACE's failure remains poorly understood.
- Although acute hypoxia and significant tumor necrosis occurs following TACE, the tumor adaptive response and localization for such have not been well characterized.
- Imaging tools using a hypoxia-specific tracer [¹⁸F] FMISO may help identify the pattern and distribution of acute post-TACE tumor hypoxia relative to demonstrated tumor progression.
- The primary hypothesis of this study states that tumor progression post-TACE arises from changes in tumor phenotype induced by treatment-related hypoxia superimposed on the dynamic process of underlying tumor hypoxia.

Objectives

To determine the feasibility of hypoxic tumor identification despite relatively high liver background signal, and describe patterns of tumor hypoxia in the immediate post-TACE treatment period using PET imaging [¹⁸F] MISO uptake registered with cross-sectional imaging.

Eligibility

- Patients ≥18 years of age with inoperable primary hepatic malignancy or hepatic-dominant metastatic disease and be otherwise eligible to receive TACE treatment. Patients with hepatocellular carcinoma should have intermediate stage disease according to the BCLC staging system (Stage A4 or B).
- Patients must not have had chemotherapy or radiation therapy to liver for at least 2 weeks prior to starting study treatments.
- Patients must not have an acute, critical illness.
- Patients must not be pregnant
- Able to understand and be willing to sign a written informed consent

Design

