1 INTRODUCTION

1.1 STUDY OBJECTIVES

1.1.1 Primary Objective

To determine the feasibility of hypoxic tumor identification despite relatively high liver background signal, and describe patterns of tumor hypoxia in the immediate post-TACE treatment period using PET imaging [¹⁸F] MISO uptake registered with cross-sectional imaging.

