1.2.3 Rationale

The primary hypothesis of this study states that tumor progression post-TACE results from changes in tumor phenotype induced by sublethal treatment-related hypoxia. The goal of the proposed pilot study is to test the feasibility of hypoxia imaging of the liver post-TACE. Early imaging detection of residual hypoxic tumor acutely following TACE may ultimately correspond to undertreated tumor and could be used to optimize TACE outcomes with targeted combinational therapies.

This pilot study will evaluate fifteen patients who will receive TACE therapy for primary or metastatic hepatic malignancy. They will undergo PET imaging of the liver with [¹⁸F] FMISO to: 1) determine the feasibility of hypoxic tumor identification despite relatively high liver background signal, and 2) identify the pattern and distribution of acute post-TACE tumor hypoxia relative to demonstrated tumor progression despite therapy. Patients will be followed according to standard community practice with conventional cross-sectional imaging (CT and/or MRI) to confirm tumor progression. Image fusion analysis will be performed to determine degree of correlation between focal hypoxia and site(s) of progression.

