3 STUDY IMPLEMENTATION

3.1 STUDY DESIGN

Fifteen patients with metastatic or primary hepatic malignancy will be enrolled to yield a minimum of ten evaluable patients. Prior to TACE, all patients will undergo conventional baseline imaging. The first five patients enrolled will receive a single dose of the study imaging agent (FMISO) post-TACE to determine imaging parameters and feasibility. Subsequent to the feasibility study, the remaining patients (#6-15) will receive the hypoxia imaging agent before and following TACE to determine changes in uptake pattern attributable to arterial embolization. Following TACE patients will be monitored according to standard of care until tumor progression is documented. Registration of functional and/or metabolic imaging demonstrating progression with immediate post-TACE hypoxia imaging will be performed for correlative analysis.

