3.3 IMAGE ANALYSIS

Feasibility of FMISO PET imaging post-TACE will be assessed by individually characterizing FMISO uptake in treated tumors as absent, background (equivalent to normal liver), or increased relative to liver background. Lesions demonstrating any increased activity compared to background liver will be further characterized as diffusely or focally increased activity.

Changes in FMISO PET activity before and following TACE will be descriptively compared and change in peak SUV will be assessed as response to embolization.

Individual liver tumors which demonstrate progression defined by increased size and/or enhancement will be evaluated for geographic FMISO uptake correlation. CT or MRI images demonstrating progression will be registered with FMISO PET-CT images automatically using OncoNav software (developed at the Center of Interventional Oncology) to determine whether qualitatively increased or decreased FMISO uptake is observed in spatial relation to tumor progression.

Increased FMISO activity which correlates positively with tumor progression will be further quantified using calculated standardized uptake values (SUV) or tumor-to- serum activity ratio in manually selected regions of interest (ROI).

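### Section 3.3 relates FMISO uptake to progression only in tumors that progress and quantifies only matching uptake, so that step cannot compare them with treated tumors that did not progress

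*Combined protocol and SAP*

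**What the plan says.** The stated objective in section 1.1.1 is about feasibility and pattern: "To determine the feasibility of hypoxic tumor identification despite relatively high liver background signal", plus a description of hypoxia soon after TACE. The Précis (Design) and section 1.2.3 add a second aim, to relate acute post-TACE hypoxia to later progression. Section 1.2.3 puts it this way: "Image fusion analysis will be performed to determine degree of correlation between focal hypoxia and site(s) of progression". The hypothesis behind it, in the same section, is that "tumor progression post-TACE results from changes in tumor phenotype induced by sublethal treatment-related hypoxia".

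Section 3.3 contains four pieces of analysis:

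- Uptake in treated tumors is graded absent, background or increased, for feasibility.
- Where there are scans before and after TACE, "change in peak SUV will be assessed as response to embolization". Section 3.1 limits paired scans to later enrollees: "the remaining patients (#6-15) will receive the hypoxia imaging agent before and following TACE".
- For progression, "Individual liver tumors which demonstrate progression defined by increased size and/or enhancement will be evaluated for geographic FMISO uptake correlation". CT or MRI showing progression is registered to the FMISO scan, and uptake related to the progression site is read as increased or decreased.
- Then "Increased FMISO activity which correlates positively with tumor progression will be further quantified using calculated standardized uptake values" or a tumor-to-serum ratio, in manually selected regions of interest.

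Sections 3.1 and 6.1 describe the correlative work in the same terms, starting from documented progression. Section 6.2.3 follows all targeted tumors for response and progression. Section 8 adds no analysis.

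**The concern.** The uptake-progression step selects twice. It first selects on the outcome, because only tumors that progressed enter. It then selects on the answer, because only increased uptake already judged to match progression is measured. Regions are drawn by hand, with no stated timing or blinding. The only masking described is the removal of identifiers from fused images (section 6.1).

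A report that follows this text gives the share of progressing tumors with increased uptake, and SUVs for the matching ones. It does not say how often treated tumors that stayed controlled had the same uptake. Section 1.2.3 hopes that early residual hypoxia may mark undertreated tumor, and a reader weighing that idea would want both figures.

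**Working it through.** The plan states no sample-size derivation, power or correlation figure on this point, so there is none to reproduce. The check sets the sections side by side and then uses labelled illustrations.

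**1. Which tumors have which data.**

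| Item | Tumors covered | Set against progression? |
|---|---|---|
| Uptake grade (3.3) | Treated tumors | No |
| Change in peak SUV (3.3, 3.1) | Patients #6-15 | No, read as response to embolization |
| Spatial read, increased or decreased (3.3) | Progressing tumors | Yes |
| SUV or tumor-to-serum ratio (3.3) | Matching increased uptake only | Yes |
| Response and progression (6.2.3) | Targeted tumors | No link to uptake |

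The two sides of a comparison are largely collected, but no section joins them. Evaluability (6.2.1.2) requires a follow-up visit with CT or MRI, not progression, so non-progressing tumors belong to the evaluable set.

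**2. Who lacks an SUV.** Patients #1-5 have one post-TACE scan and no paired comparison. That is 5 of 15 planned, and up to 5 of the minimum 10 evaluable. The tumor-to-serum ratio in section 3.2 is only a technique that may be used.

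**3. Illustration with assumed counts.** Take 20 treated lesions, with 60% of progressing lesions showing increased uptake. Progression among increased lesions = (increased and progressed) / (all increased), and likewise for lesions not increased.

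| Progressing | Step reports | Non-progressing with increased uptake | Progression, increased | Progression, not increased |
|---|---|---|---|---|
| 10 | 6/10 | 2/10 | 6/8 = 75% | 4/12 = 33% |
| 10 | 6/10 | 6/10 | 6/12 = 50% | 4/8 = 50% |
| 10 | 6/10 | 9/10 | 6/15 = 40% | 4/5 = 80% |
| 15 | 9/15 | 1/5 | 9/10 = 90% | 6/10 = 60% |
| 15 | 9/15 | 3/5 | 9/12 = 75% | 6/8 = 75% |
| 15 | 9/15 | 4/5 | 9/13 = 69% | 6/7 = 86% |

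In each block the reported figure is fixed while the association runs from positive through none to negative.

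**4. Same check at the minimum evaluable size.** Assume one tumor in each of 10 patients, 6 progressing, 4 of those with increased uptake. The phi coefficient is (ad − bc)/√(product of the four margins), where a, b are progressing tumors with and without increased uptake and c, d are non-progressing tumors with and without it.

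- 0 of 4 non-progressing increased: (4×4 − 2×0)/√(4×6×6×4) = 16/24 = +0.67
- 2 of 4 increased: (4×2 − 2×2)/√(6×4×6×4) = 4/24 = +0.17
- 4 of 4 increased: (4×0 − 2×4)/√(8×2×6×4) = −8/19.6 = −0.41

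The planned step reports 4/6 in all three. Even the first case gives a Fisher p of 0.08, so such a table describes and does not test.

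**5. Scans without uptake above liver.** Section 3.5.2 calls a scan deficient, leaves it out of the analysis and replaces the patient if, in the investigator's opinion, it shows no hepatic uptake relative to liver background. Section 3.3 has two grades, absent and background, for tumors on such scans. Section 6.2.3 wants conclusions based on all eligible patients. The wording of 3.5.2 may be meant for technical failures. Read literally, it removes the negatives, and the feasibility denominator is then affected too.

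**6. Time to measure before outcome is known.** Post-TACE FMISO is at 24 to 72 hours (section 3.4) and the first follow-up CT/MRI is due at 4 to 6 weeks (section 3.1.3). At the tightest, 28 − 3 = 25 days.

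**The case against.** The strongest reply is that the plan asks a spatial question. Sections 1.2.3, 3.3 and 6.1 speak of sites, geographic correlation and overlap. That is co-localization inside a tumor, whose natural reference is the rest of the same tumor, and a tumor without a progression site cannot enter it. This stands, and it makes the missing within-tumor reference region the nearer gap. It does not close the other one, because the Précis and section 1.2.3 also state the wider aim of relating acute hypoxia to demonstrated progression.

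Second, this is a proof-of-concept pilot whose only listed objective is feasibility and pattern. That stands too, and it limits the severity. A descriptive report can still show the non-progressing row.

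Third, discordant uptake is not ignored, since the spatial read allows decreased as well as increased uptake. That holds only within progressing tumors, and discordant uptake is not quantified in that step.

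Fourth, a whole-lesion table would be hard to read. Section 1.2.1 says TACE causes significant necrosis and section 10.8 says FMISO is not trapped in necrotic tissue, so low uptake may mean dead or well-oxygenated tissue. The comparison group may also be small, because patients are followed until progression. Both limits stand and should be stated with the table.

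**Conclusion.** The point holds and is minor. Followed as written, section 3.3 describes overlap within progressing tumors. It cannot show whether uptake is more frequent or higher where treated tumors progress. This rests on the text. The counts in the illustrations are assumed and show only that the reported share leaves the direction of any association open.

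Three stronger readings are tempting, and the documents do not support them:

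- **That the study has no comparator of any kind.** Treated tumors are graded, targeted tumors are followed, and paired patients have peak SUV change. What is missing is a planned link, plus SUVs for patients #1-5 outside matching uptake.
- **That the primary objective fails.** Grading all treated tumors serves that objective regardless of progression. Only the exclusion reading of section 3.5.2 would reach it, and that wording is ambiguous.
- **That choosing matching lesions inflates the SUVs by a calculable amount.** The documents give no SUV distribution. Lesions picked for being above liver have higher SUVs even if uptake is unrelated to progression, so a high mean would not by itself reveal selection for concordance.

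**What to change.** Amend section 3.3 as follows:

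1. Measure peak SUV in every treated lesion on the post-TACE 120-minute scan under one region-of-interest rule, and the tumor-to-serum ratio where serum activity is available. Draw the regions before follow-up CT/MRI is read.
2. Tabulate uptake category and SUV by lesion-level progression for all treated lesions, showing patient and follow-up time. State one lesion-level progression rule: section 3.3 gives no threshold, and the 20% rule in section 6.2.3 applies to a sum of diameters.
3. In progressing tumors, compare uptake at the progression site with the rest of the same tumor.
4. Reconcile section 3.5.2 with sections 3.3 and 6.2.3 so that technically adequate scans graded absent or background stay in the analysis.
5. Label all of this descriptive, with no test, and note that low uptake may reflect necrosis as well as oxygenated tissue.

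The cost is extra region-of-interest work on one post-TACE session per patient (5 + 10 = 15 planned, more if patients are replaced), the within-tumor comparison, and one table. No new scan or sample is needed. The comparison group may be small if most lesions progress, and concordance may look weaker than under the present text. The regions should be drawn in the first weeks after TACE, because they cannot be made blind to outcome later.

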3.4 STUDY CALENDAR

Patients will be scheduled for pre-TACE imaging up to one week before TACE and post-TACE imaging 24 to 72 hours based on their clinical condition. Patients will sign the protocol consent prior to [¹⁸F] FMISO administration and imaging. Per PET scanning protocols, patients will be NPO (≥4-6 hours) before actual scanning. Patients will obtain standard of care post-TACE imaging by their primary oncology team, however, the research team may follow up, typically, but not required with clinic visits or phone calls. Follow up imaging and tumor measurements/s are the only research-related activities to be performed until tumor progression, withdrawal from study or a new, non-TACE, treatment is indicated. If this follow-up occurs outside NIH CC, documentation must be provided to the study PI.

	Pre- ^[18F] FMISO PET Scan	^[18F] FMISO PET Scan ^{4,5}	Standard of Care and Research follow up post TACE ^{3,4,7}
Informed consent ¹	X		
^[18F] FMISO dose approximately 10mCi ⁴		X	
Primary or metastatic malignant hepatic disease ²	X		
CT/ MRI ⁴	X		X

Tumor measurements ^{4,8}	X		X
Demographics ⁴	X		
Medical history ⁴	X		X
Physical exam ⁴	X		X
Vital signs ⁴	X		X
Height ⁴	X		
Weight ⁴	X		
Creatinine ⁴	X		
B-hCG Urine or Serum ^{3,6}	X		
Adverse event evaluation		X ³	X

1. Informed consent must occur prior to any study specific procedure or scan. See also section 9.4
2. In the absence of a pathological diagnosis of hepatocellular carcinoma, the diagnosis shall be made by the combination of serum alpha-fetoprotein ≥ 200 mg/ml and CT or MRI of the liver showing an imaging appearance characteristic of hepatocellular carcinoma
3. AE evaluation will be obtained within 24 hours post TACE FMISO injection.
4. Patient must have physician willing to collaborate with NIH PI by providing required medical record and digital MR/ CT scan documentation pre and post TACE procedure. Imaging done outside NIH must be digitally provided to NIH for tumor measurement/assessment
5. NIH only
6. FMISO imaging will be performed **only** post TACE in **the first five consecutively enrolled patients** and pre and post TACE in the **remaining** patients.
7. Pregnancy test for women of childbearing potential. Test must be within 48 hours of PET scan
8. Standard of care follow up post- TACE q 4-6 weeks. Scanning interval may be increased to 3 months if stable disease is documented on at least two successive imaging studies
9. Imaging done outside NIH digitally provided to NIH for tumor measurement/assessment

3.5 CRITERIA FOR REMOVAL FROM PROTOCOL AND OFF STUDY CRITERIA

3.5.1 Off Treatment

Patient will be considered “off treatment” 24 hours following post-TACE [¹⁸F] FMISO injection. No research-related follow up such as adverse event monitoring, will take place after this time period.

3.5.2 General Off-Study Criteria

- Inability to complete ¹⁸F-MISO imaging
 - Patients will be considered “unevaluable” for the study if [¹⁸F] FMISO imaging is incomplete or deficient and will be replaced (see Section 6.2.1). As an example, an FMISO scan which in the opinion of the Principal Investigator does not demonstrate hepatic uptake relative to background liver activity will be considered deficient and will not be included in the data analysis.
- Patient decides to withdraw from the study

- Toxicity which prevents further imaging (e.g. renal dysfunction defined as serum creatinine >2.0mg/dl which precludes CT or MRI imaging)
- Death
- Progression of disease
- Additional treatment of primary or metastatic hepatic malignancy (i.e., transplantation, resection)

The reason for study removal and the date the patient was removed must be recorded in the study database.

3.6 FOLLOW-UP

Research-related follow up may be obtained outside NIH CC as part of routine pre- and post-TACE care. Patient must have physician willing to collaborate with NIH PI by providing required medical record and digital MR/ CT scan documentation pre and post TACE procedure. Imaging done outside NIH must be digitally provided to NIH for tumor measurement/assessment.

Primarily, after the patient is considered “off treatment”, research-related follow-up consists of standard of care post-TACE imaging which is q 4-6 weeks. Scanning interval may be increased to 3 months if stable disease is documented on at least two successive imaging studies

Other typical, but not required, evaluations may also include clinical visits, phone calls from the research team, and laboratory testing.

3.7 STUDY STOPPING RULES

Enrollment will be halted; IRB will be notified if:

- Any grade 3 adverse event definitely attributed to [¹⁸F] FMISO (occurring within 24 hours of injection)
- Any grade 4 or grade 5 adverse event regardless of attribution
- Patients not receiving TACE at NIH CC will be observed for adverse events according to one or more of the following:
 - Patient must have physician willing to collaborate with NIH PI by providing required medical record and digital MR/ CT scan documentation pre and post TACE procedure
 - patients will be provided with the PI’s contact information to report symptoms which could represent an adverse event,
 - telephone call from the PI’s designee on the day following the FMISO scan to document signs or symptoms
- Patient(s) will be monitored until there is improvement or resolution of toxicity.
- Following review and approval by the IRB study enrollment will resume.

Enrollment will be limited to six patients if fewer than 2 patients demonstrate demonstrable ¹⁸F-FMISO uptake in liver tumors, consistent with diagnostic uptake of radiopharmaceutical in fewer than 30% of patients with liver cancer.

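### Paired scanning opens at patient 6, but the only numerical feasibility rule is set at six patients, so patient 6 has a pre-TACE research scan before the rule can be read at its stated number

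*Combined protocol and SAP*

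**What the plan says.** Section 3.1 describes two stages. The first: "The first five patients enrolled will receive a single dose of the study imaging agent (FMISO) post-TACE to determine imaging parameters and feasibility". The second: "Subsequent to the feasibility study, the remaining patients (#6-15) will receive the hypoxia imaging agent before and following TACE". A note to the calendar in section 3.4 repeats the split, restricting FMISO to the post-TACE scan in "the first five consecutively enrolled patients" and giving the others both scans. Section 3.4 also sets the timing: the pre-TACE scan falls up to one week before TACE, the post-TACE scan 24 to 72 hours after it.

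Section 3.7 holds the only numerical feasibility criterion: "Enrollment will be limited to six patients if fewer than 2 patients demonstrate demonstrable" FMISO uptake in liver tumours, a result described as "consistent with diagnostic uptake of radiopharmaceutical in fewer than 30% of patients with liver cancer". It does not name the scan that is counted. Section 3.3 says how feasibility is judged: "Feasibility of FMISO PET imaging post-TACE will be assessed by individually characterizing FMISO uptake in treated tumors". Section 8 adds no criterion and says that power and significance calculations do not apply.

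**The concern.** The second stage is presented as following a completed feasibility study, but the rule that judges feasibility is expressed in six patients, and the sixth belongs to the second stage. Nothing in the protocol gives a criterion at five, or holds patient 6 until the first five have been read.

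At stake is an additional radiotracer injection and CT for one patient, in a study that section 9.3.2 says offers participants no direct benefit, at a time when feasibility may be undecided or already unattainable. There is also a matter of clarity: in a 15-patient study without a power calculation, this rule is the only quantitative feasibility check, so when it is read should not be in doubt.

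**Working it through.** **1. The rule's own figure.** One of six is 1/6 = 16.7%, below 30%. Two of six is 2/6 = 33.3%, above it. Fewer than 2 of 6 therefore matches the 30% description in section 3.7, and the rule is internally sound.

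**2. Order of events.** Patient 6's pre-TACE scan comes before TACE, and the post-TACE scan at least 24 hours after it. The sixth post-TACE result can never be available when the pre-TACE injection is given.

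**3. What the first five already settle.** Let X be the number of the first five with uptake.
- X = 0: the most that six patients can give is 1, so the rule cannot be met.
- X = 1: patient 6 decides the outcome.
- X of 2 or more: the rule is met before patient 6 is scanned.

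The pre-TACE scan of patient 6 is premature in the first two cases only.

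**4. How often.** The true uptake rate p is not given in the documents, so a range is shown, assuming independent patients with a common p. The formulas are P(X = 0) = (1 − p)^5 and P(X = 1) = 5p(1 − p)^4. At p = 0.3 these give 0.7^5 = 0.168 and 5 × 0.3 × 0.7^4 = 0.360, in total 0.528.

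| True rate p | X = 0 | X = 1 | X = 0 or 1 | X ≥ 2 (rule already met) |
|---|---|---|---|---|
| 20% | 0.328 | 0.410 | 0.737 | 0.263 |
| 30% | 0.168 | 0.360 | 0.528 | 0.472 |
| 40% | 0.078 | 0.259 | 0.337 | 0.663 |
| 50% | 0.031 | 0.156 | 0.188 | 0.813 |

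**5. Dose of the extra scan.** Section 9.3.1.1 gives an effective dose of 0.013 to 0.014 mSv/MBq. For the activity I take 70 kg × 3.7 MBq/kg = 259 MBq as the low value and 10 mCi × 37 MBq/mCi = 370 MBq as the high value. FMISO then contributes 0.013 × 259 = 3.4 mSv to 0.014 × 370 = 5.2 mSv. The CT is stated to be less than 6 mSv, with no lower figure, so the sum is below 5.2 + 6 = 11.2 mSv.

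**6. Effect of moving the look instead of the stage.** The chance of stopping at six is (1 − p)^6 + 6p(1 − p)^5, which at p = 0.3 is 0.118 + 0.303 = 0.420. Reading the same threshold at five still straddles 30% (1/5 = 20%, 2/5 = 40%), but the chance of stopping at p = 0.3 becomes 0.528.

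**The case against.** The best defence is that the two numbers serve different purposes. The five-patient stage sets imaging parameters as well as feasibility, while section 3.7 caps total enrolment and says nothing about pre-TACE injections, so the boundaries need not coincide. The rule also needs fewer than six results once two patients show uptake. At a true rate of 30% that has happened by patient 5 in 47% of trials, and at 50% in 81%. Only one patient is affected, and section 9.3.1.1 puts the study's radiation below the 5 rem (50 mSv) annual guideline.

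Most of this stands and limits the size of the point. It does not remove it: section 3.1 itself makes the paired stage follow a feasibility study, and no other numerical criterion exists by which that study could be judged complete at five.

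A reader might go further and infer that patient 6, having two scans, has two chances to count as positive, so that stopping is less likely than the rule implies. The documents do not support that. Section 3.3 ties feasibility to post-TACE imaging, all six patients are due that scan, and nothing lets a pre-TACE scan count. Any figure for such a bias would also have to treat two scans of the same tumours as independent, which is implausible. What remains is that section 3.7 leaves the counted scan unnamed.

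**Conclusion.** The mismatch between a stage boundary at five and a rule at six is real, and minor. It leads to a premature research scan of one patient in about 53% of trials at a true uptake rate of 30%, 34% at 40% and 19% at 50%. In 17% of trials at a true 30%, that scan happens although the rule can no longer be met. It would be too strong to say that every trial is affected, since two or more positives among the first five already satisfy the rule.

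These figures assume independent patients, a common uptake rate, first-five results that are known before patient 6 is scanned, and that the six counted are the first six enrolled. The last assumption is not certain: section 3.5.2 says that a scan which "does not demonstrate hepatic uptake relative to background liver activity will be considered deficient and will not be included in the data analysis", and such patients are replaced, so the text does not settle whether the rule counts enrolled or evaluable patients. Without a pause after patient 5, the third assumption may also fail, and the scan would then be premature more often.

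**What to change.** Reconcile sections 3.1, 3.4 and 3.7 so that no pre-TACE FMISO scan is done until the feasibility rule has been met. The simplest wording makes patients 1 to 6 the post-TACE-only stage and patients 7 to 15 the paired stage. Section 3.7 should add that uptake is counted on the post-TACE scan, in line with section 3.3, and whether the six are enrolled or evaluable patients.

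The change takes about one sentence in each section. It leaves nine paired patients instead of ten for a comparison that section 3.3 describes as descriptive, and a possible short wait while the sixth scan is read. Total enrolment of 15 and the rule's stopping probabilities do not change.

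If the boundary must stay at five, the alternative is to read the rule at five. That keeps ten paired patients but raises the chance of stopping at a true 30% from 42% to 53%, so it is the costlier choice.
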